6.4.5 Handling of Missing Data

¹ Lehr, R. G. 2001. Some practical considerations and a crude formula for estimating sample size for McNemar's test. Drug Information Journal, 35: 1227-1233.

Missing data will be maintained as missing in the analysis datasets, unless specified otherwise. If it is deemed that imputing data is necessary, the analysis dataset will contain a new variable with the imputed value and the original variable value will be maintained as missing.

7 - Trial Administration

7.1 Ethical Considerations: Informed Consent and HIPAA Authorization

The study will be conducted in accordance with the ethical principles that have their origin in the Declaration of Helsinki. Informed consents will be scanned into the patient's chart and hard copy will be stored in a locked file draw/cabinet at NYU Langone RSOFNY. The PI and sub-investigators will have access to the locked storage unit.

Data will be stored using codes assigned by the investigators in an excel spreadsheet. The data will be collected and stored on REDCap. Only investigators will have access to the samples and data.

There is not any foreseeable possibility that a previously unknown condition (disease, genetic disposition, etc.) will be discovered as the result of the study procedure.

Additional information as a result of this study will be added to the patient's medical record and include the use of ZyMot to process the sperm specimen and post-processing sperm parameters.

7.2 Institutional Review Board (IRB) Review

The protocol, informed consent form(s), recruitment materials, and all participant materials will be submitted to the IRB for review and approval. Approval of both the protocol and the consent form will be obtained prior to enrolling any participants. Any amendment to the protocol will require review and approval by the IRB before the changes are implemented to the study. All changes to the consent form will be IRB approved.

7.3 Subject Confidentiality

All data will be stored and analyzed in accordance with NYU's policy on retention of and access to research data. Potential identifiable information (patient and cycle ID) will be recorded as a numerical number. All research data will be maintained in tangible form and will be retained by the principal investigator and other researchers in confidential and secure storage space owned or controlled by NYU Langone Health and approved by NYU Langone Health's Medical Center Information Technology (MCIT) department. The data will be stored for 6 years after manuscript completion. It will be destroyed by deleting it from the storage space. All Research Data containing protected health information will be maintained in accordance with New York State laws and regulations.

All hard copies of the informed consents will be stored in a locked file cabinet at the study site and only the investigators will have access to the cabinet.

7.4 Deviations/Unanticipated Problems

Protocol deviations are any noncompliance with the clinical trial protocol. The deviation may be either on the part of the participant, the investigator, or the study site staff.

It will be the responsibility of the principal investigator to use continuous vigilance to identify and report deviations promptly from the time the investigator becomes aware of the event. All protocol deviations will be addressed in study source documents, and reported to the sponsor and to the local IRB per the guidelines.

7.5 Data Collection

Data collection will be the responsibility of the study staff at the site under the supervision of the site PI. The investigator will be responsible for ensuring the accuracy, completeness, legibility, and timeliness of the data reported. Information pertinent to this project will be available in the electronic

medical records, clinic records, and a subject datasheet. A study investigator will record demographic data and related medical data on the subject datasheet.

All data will be stored and analyzed in accordance with NYU's policy on retention of and access to research data. Potential identifiable information (patient and cycle ID) will be recorded as a numerical number. All research data will be maintained in tangible form and will be retained by the PI and other researchers in confidential and secure storage space owned or controlled by NYU Langone Health and approved by NYU Langone Health's Medical Center Information Technology (MCIT) department. The data will be stored for 6 years after manuscript completion. It will be destroyed by deleting it from the storage space. All Research Data containing protected health information will be maintained in accordance with New York State laws and regulations.

All hard copies of the informed consents will be stored in a locked file cabinet at the study site and only the investigators will have access to the cabinet.

7.6 Data Quality Assurance

The study investigators will be responsible for implementing and maintaining quality assurance and quality control systems to ensure that the trial is conducted and data are generated, documented (recorded), and reported in compliance with the protocol, GCP, and the applicable regulatory requirement(s).

The study investigators will be responsible for securing agreement from all involved parties to ensure direct access to all trial-related sites, source data/documents, and reports for the purpose of monitoring and auditing by the sponsor, and inspection by domestic and foreign regulatory authorities.

Quality control will be applied to each stage of data handling to ensure that all data are reliable and have been processed correctly.

Agreements, made by the sponsor with the investigator/institution and any other parties involved with the clinical trial, will be in writing, as part of the protocol or in a separate agreement.

7.7 Study Records

Study records will include patient consents, protocols, electronic medical records, and data related to the study.

7.8 Access to Source

Access to study records will be limited to IRB-approved members of the study team. All data will be stored and analyzed in accordance with NYU's policy on retention of and access to research data. Potential identifiable information (patient and cycle ID) will be recorded as a numerical number. All research data will be maintained in tangible form and will be retained by the PI and other researchers in confidential and secure storage space owned or controlled by NYU Langone Health and approved by NYU Langone Health's Medical Center Information Technology (MCIT) department. The investigator will permit study-related monitoring, audits, and inspections by the IRB/EC, the sponsor, government regulatory bodies, and university compliance and quality assurance groups of all study related documents (e.g., source documents, regulatory documents, data collection instruments, study data etc.). Data may be shared with the sponsor of the study; however, data will be de-identified prior to sharing the data.

7.9 Data or Specimen Storage/Security

All data will be stored and analyzed in accordance with NYU's policy on retention of and access to research data. Potential identifiable information (patient and cycle ID) will be recorded as a numerical number. All research data will be maintained in tangible form and will be retained by the PI and other researchers in confidential and secure storage space owned or controlled by NYU Langone Health and approved by NYU Langone Health's Medical Center Information Technology (MCIT) department.

All Research Data containing protected health information will be maintained in accordance with New York State laws and regulations.

All hard copies of the informed consents will be stored in a locked file cabinet at the study site and only the investigators will have access to the cabinet.

7.10 Retention of Records

All data will be kept for 6 years following completion of the study. If permission is needed to move or destroy the records, it will be the PI's responsibility.

7.11 Study Monitoring

Halfway through recruitment of sample size, preliminary results will be analyzed to by the principal investigator and co-investigators. Information related to the study will be periodically evaluated for accuracy by one or more of the study investigators.

7.12 Data Safety Monitoring Plan

Halfway through recruitment of sample size, preliminary results will be analyzed by the principal investigator and co-investigators. If the primary endpoint is adversely affected by study arm, the study will be terminated. The primary endpoint will be percentage of good quality embryos comparing those inseminated with density processed sperm and ZyMot processed sperm. In the event that there is a statistically significant ($p < 0.05$) percentage of higher quality embryo formation in the embryos created via sperm inseminated with density processed sperm compared to ZyMot processed sperm, the study will be terminated. Preliminary analysis of the results will be communicated promptly to the IRB.

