6.3.3 Screening

All patients/donor dyads potentially undergoing ICSI and meeting inclusion criteria for the study will be approached to participate in the study. Screening will be performed by study investigators at NYU Langone Reproductive Specialists of NY.

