6.3.4 Recruitment, Enrollment and Retention

Recruitment into the study will be performed by a study investigator at NYU Langone RSOFNY. Patient/sperm source dyads are recruited from the study investigators' practice (RSOFNY) during a routine clinical visit. If patient/sperm source dyads desire to enroll in the study, it will be denoted in their medical record chart. If they meet eligibility criteria on the day of oocyte retrieval (no evidence of severe male factor infertility or surgically derived sperm, at least 6 mature oocytes available for randomization, and possibility for ICSI insemination) the study will be performed as per study protocol.

In the event that the patient consented to the study but the provided semen sample on the day of oocyte retrieval shows severe male factor infertility. The patient/sperm source dyad will then be withdrawn from the study since the sample will not qualify for preparation via ZyMot nor density gradient.

In the event that the patient/sperm source dyad consented to the study but does not meet the inclusion criteria of ICSI insemination or at least 6 mature oocytes available for insemination, insemination will occur only with the sperm separated via density gradient, however, the sperm parameters following ZyMot and density gradient sperm separation will be recorded. The data on sperm parameters after sperm separation via ZyMot and density gradient will still be collected but the patient/sperm source dyad will have no further participation in the study.

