6.4 Statistical Method

6.4.1 Statistical Design

All data will be de-identified and then will be analyzed by a statistician. Descriptive statistics of the study sample will be calculated (mean \pm standard deviation or median [25th, 75th percentiles] for continuous variables; frequency and percent for categorical data. Paired analyses will be performed. A result will be considered statistically significant at the $p < 0.05$ level of significance. All analyses will be performed using SAS version 9.4 (SAS Institute Inc., Cary, NC).

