6.4.3.5 Interim Analysis

An interim analysis will be performed at the midway point of oocyte recruitment. Interim analysis will evaluate percentage of good quality embryo formation. Study will be terminated in the event that there is a significant decrease in good quality embryo formation in the study arm compared to the control arm.

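### The half-way by-arm result on the primary endpoint goes to the investigators who continue the trial; sections 7.11 and 7.12 should be reconciled with 6.4.1, and the team told only stop or continue

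*Combined protocol and SAP*

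**What the plan says.** Section 7.12 states that half-way through recruitment "preliminary results will be analyzed by the principal investigator and co-investigators". Section 7.11 repeats it: "preliminary results will be analyzed to by the principal investigator and co-investigators". Section 6.4.3.5 sets the same look, "An interim analysis will be performed at the midway point of oocyte recruitment", names no analyst, and fixes the content: "Interim analysis will evaluate percentage of good quality embryo formation".

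The decision is one-directional. Under 6.4.3.5, 7.12 and 7.14 the study ends if the ZyMot arm is significantly worse (p < 0.05 in 7.12); otherwise it goes on. Section 7.12 also has the interim results sent to the IRB.

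Section 6.4.1 gives a different general arrangement: "All data will be de-identified and then will be analyzed by a statistician". Sections 7.11 and 7.12 do not mention that role.

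Investigators also screen (6.3.3) and recruit (6.3.4: "Recruitment into the study will be performed by a study investigator"), and one or more of them check data accuracy (7.11). No independent committee, and no limit on who within the team sees the interim comparison, is described.

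**The concern.** Someone who knows which arm is ahead at the mid-point, and who can still influence how outcomes are produced or recorded, is a source of operational bias. Three features of this plan make that relevant.

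- The endpoint depends on judgement: section 5.2.1 counts a day 5 or 6 blastocyst if its overall grade is good or fair.
- The arm is visible at grading. Section 6.1.2 describes no masking and says droplet numbers trace back to the sperm preparation used.
- Some laboratory steps leave discretion. The patient-number rule in 6.1.3 fixes recording order and who receives an odd extra oocyte, but not which individual oocyte goes to which half. Embryo choice for transfer (6.1.2) bears on the secondary pregnancy outcomes.

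At stake is the credibility of the second half of the data, and of a positive result in a trial funded by the device manufacturer (7.17).

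**Working it through.** **1. The passages side by side.** Section 6.4.1: all data, analysed by a statistician after de-identification. Sections 7.11 and 7.12: interim data, analysed by the investigators. Section 6.4.3.5: analyst not named. One reading is that the statistician computes and the investigators review; the other is that the investigators do the analysis. Under both, the investigators see the comparison.

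**2. The plan's own figure.** Section 6.4.2 gives n = 16pq(1−r)/d², with rates of 48% and 55% (p = 0.515, q = 0.485), r = 0.5 and d = 0.07:

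16 × 0.515 × 0.485 × 0.5 / 0.0049 = 407.8, rounded up to 408. The stated figure reproduces.

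**3. Standard error of the paired difference.** The plan states none, so it is derived from the same inputs.

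Variance per pair = 0.48×0.52 + 0.55×0.45 − 2×0.5×√(0.48×0.52×0.55×0.45) = 0.2486.

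- 408 read as pairs: √(0.2486/408) = 0.0247, or 2.5 points.
- 408 read as single oocytes, so 204 pairs: √(0.2486/204) = 0.0349, or 3.5 points.

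The text speaks of a total of 408 oocytes split in half, so both readings are carried forward.

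**4. Effect of an assumed grading shift.** Suppose there is no true difference and grading moves by s points in favour of one arm, in the second half only. The final difference shifts by s/2, and the two-sided false-positive rate is P(|Z + (s/2)/SE| > 1.96).

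| Assumed shift s | Shift in final difference | 408 pairs | 204 pairs |
|---|---|---|---|
| 0 | 0 | 5.0% | 5.0% |
| 1 point | 0.5 point | 0.005/0.0247 = 0.20 → 5.5% | 0.005/0.0349 = 0.14 → 5.2% |
| 3 points | 1.5 points | 0.015/0.0247 = 0.61 → 9.3% | 0.015/0.0349 = 0.43 → 7.1% |

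A 1.5-point shift is 1.5/7 = 21% of the targeted difference. The documents give no basis for any value of s.

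**5. How informative the interim is.** At half the information, conditional power under the design effect is P(Z > (1.96 − z√0.5 − 0.5θ)/√0.5), where z is the interim statistic and θ = 0.07/SE. With 408 pairs θ = 2.84, giving about 22% at z = 0, 59% at z = 1 and 88% at z = 1.96. With 204 pairs θ = 2.01, giving about 9%, 36% and 73%. Investigators who continue would have a fair idea of whether the trial is heading for success.

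**6. What the look does not do.** Because the rule stops only for harm, the chance of a false claim of benefit stays at about 0.025 (simulated 0.0251). The concern is about access to the result and does not involve alpha spent on benefit.

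**The case against.** **Patient selection.** A reader might infer that investigators who know the trend could favour an arm through whom they approach. The documents do not support this. Every dyad supplies oocytes to both arms (6.1.2, 6.1.3), and 6.3.3 has all eligible dyads approached. This objection stands in full. The choice of ICSI over IVF is likewise made for the whole dyad.

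**Who grades.** A reader might also infer that those who see the interim are those who grade. The documents do not say so: grading is described without naming the grader, and embryology staff appear separately (4.3, 6.3.1). What remains is that nothing stops the result reaching them. Unmasked grading is the underlying weakness, it exists from the first patient, and masking would address it more directly. Restricting interim access would still matter for the other discretionary decisions.

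**Contradiction.** It is tempting to call 6.4.1 and 7.11–7.12 contradictory. Section 6.4.1 is a general statement and the two can be read together, so this is a tension to resolve.

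**Data already in hand.** Section 6.1.2 logs the two preparations as separate samples and links oocyte number to arm, an investigator records data (7.5), and 7.1 limits data access to investigators. At a single site they could tally outcomes at any time, and de-identification is not said to conceal arm. This also stands: a stop/continue message withholds the formal comparison but is not a complete firewall.

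**Reporting duties.** Section 6.2.2.1 requires researchers to report new information on risks or benefits to the IRB within 5 working days. That does not require the team to see the comparison, but the route must be written so that the duty is met.

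**Conclusion.** The concern holds as a matter of interim access. The plan gives the by-arm primary result to people who continue running the trial, although the only decision is a binary harm rule and a statistician is already named. The plausible route to bias is the result reaching unmasked graders or others with laboratory discretion.

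The size is unknown. Under assumed second-half shifts the false-positive rate is about 5.2–5.5% for 1 point and about 7% (204 pairs) to 9% (408 pairs) for 3 points, against 5%. These figures rest on the plan's rates and r = 0.5, a normal approximation, and shifts that are purely illustrative. A small shift does little harm. The case for change is that the exposure is avoidable at low cost and that knowledge, once shared, cannot be withdrawn.

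**What to change.** Amend 6.4.3.5, 7.11 and 7.12 to agree with 6.4.1:

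- A statistician with no role in recruitment, grading or embryo selection runs the interim comparison and applies the existing harm rule. Section 6.4.1 does not state such independence, so it should be added.
- The statistician sends the comparative result directly to the IRB, with wording that reconciles this with the investigators' reporting duties in 6.2.2.1.
- Investigators and embryology staff receive only *stop* or *continue*. They see the comparison if the rule is met, or at the end of the trial.
- Study staff do not tabulate outcomes by arm before the end of the trial.
- The data-access wording in 7.1 is amended so that the statistician has access.

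The sample size, alpha, interim timing and harm rule are unchanged. The cost is protocol wording in several sections, and investigators lose sight of mid-trial results. The protection is partial because they still hold the source data.

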7.13 Study Modification

If at any points study modifications are to be made, the protocol will be updated and changes submitted to the IRB. Changes to the protocol will be implemented once approved by the IRB.

7.14 Study Discontinuation

In the event that preliminary analysis reveals significantly reduced primary outcome in the experimental arm, the study will be discontinued.

7.15 Study Completion

Study will be completed when 408 oocytes are randomized which is anticipated to be in approximately 1-2 years from study commencement.

7.16 Conflict of Interest Policy

Any investigator who has a conflict of interest with this study (patent ownership, royalties, or financial gain greater than the minimum allowable by their institution, etc.) will have the conflict reviewed by the NYU Langone Conflict of Interest Management Unit (CIMU) with a Committee-sanctioned conflict management plan that has been reviewed and approved by the study sponsor prior to participation in this study. All NYULMC investigators will follow the applicable conflict of interest policies.

7.17 Funding Source

The study will be funded by DxNow Inc, manufacturer of the ZyMot device.

7.18 Publication Plan

Publication procedures and authorship will be addressed in the Clinical Trials Agreement for this study.
